8.3.7 REPORTING EVENTS TO PARTICIPANTS

The Principal Investigator and study staff will send an IRB approved letter to each study participant in the event of an AE or SAE that is determined by the IRB to change the study risks to the participant. In addition, at the completion of the study an IRB approved letter will be sent to each participant to inform them that the study is completed and provide them with information related to the study outcomes and provide a link to any research articles that are published related to this study.

8.3.8 EVENTS OF SPECIAL INTEREST

Not applicable

8.3.9 REPORTING OF PREGNANCY

Not applicable

8.4 UNANTICIPATED PROBLEMS

8.4.1 DEFINITION OF UNANTICIPATED PROBLEMS (UP)

The Office for Human Research Protections (OHRP) considers unanticipated problems involving risks to participants or others to include, in general, any incident, experience, or outcome that meets **all** of the following criteria:

- Unexpected in terms of nature, severity, or frequency given (a) the research procedures that are described in the protocol-related documents, such as the Institutional Review Board (IRB)-approved research protocol and informed consent document; and (b) the characteristics of the participant population being studied;
- Related or possibly related to participation in the research (“possibly related” means there is a reasonable possibility that the incident, experience, or outcome may have been caused by the procedures involved in the research); and
- Suggests that the research places participants or others at a greater risk of harm (including physical, psychological, economic, or social harm) than was previously known or recognized.

8.4.2 UNANTICIPATED PROBLEM REPORTING

The investigator will report unanticipated problems (UPs) to the reviewing Institutional Review Board (IRB). The UP report will include the following information:

- Protocol identifying information: protocol title and number, PI’s name, and the IRB project number;
- A detailed description of the event, incident, experience, or outcome;
- An explanation of the basis for determining that the event, incident, experience, or outcome represents an UP;
- A description of any changes to the protocol or other corrective actions that have been taken or are proposed in response to the UP.

To satisfy the requirement for prompt reporting, UPs will be reported using the following timeline:

- UPs that are serious adverse events (SAEs) will be reported to the IRB, the Safety Officer and the NIAMS, through the NIAMS contractor within 48 hours of being reported to the Investigator. The immediate reports will be followed by detailed, written reports as soon as possible as follow up information may be required before a written report can be provided. The Principal Investigator will report all serious adverse events to the study’s NIAMS safety officer on a biannual basis.
- Any other UP will be reported to the IRB and the Safety Officer and the NIAMS, through the NIAMS contractor within 10 business days if a protocol deviation/violation, or other unanticipated problem.
- All UPs should be reported to appropriate institutional officials (as required by an institution’s written reporting procedures), the Safety Officer and the NIAMS, through the

NIAMS contractor, and the Office for Human Research Protections (OHRP) within 10 business days of the IRB's receipt of the report of the problem from the investigator.]

8.4.3 REPORTING UNANTICIPATED PROBLEMS TO PARTICIPANTS

Not applicable

9 STATISTICAL CONSIDERATIONS

9.1 STATISTICAL HYPOTHESES

All statistical analysis will be completed under the direction of [name]. Depending on the outcome, change (completion-baseline), or the value at completion will be assessed, and the statistical significance of the group differences can be assessed by a t-test or the non-parametric equivalent (2-sample Wilcoxon). Standardized differences will be calculated for the purposes of powering the subsequent clinical trial.

- **Primary Efficacy Endpoint(s):**
We will test the hypothesis that our biofeedback program will decrease the risk of secondary ACL injury by improving loading and movement symmetry (knee extension moment asymmetry) during the dynamic task of landing from a jump 6 weeks post intervention.

Movement and loading symmetry will be assessed using the limb symmetry index ($LSI = \frac{ABS[Surgical] - ABS[Nonsurgical]}{0.5(ABS[Surgical] + ABS[Nonsurgical])} * 100$)^{2,3,7,34} prior to (baseline) and at two time points following (immediately following training (efficacy), and 6 weeks after (durability)) the biofeedback training program.

- **Secondary Efficacy Endpoint(s):**
No hypothesis testing will be completed for the secondary endpoint as this is a pilot clinical trial and will be used to determine the best procedures to following when planning a subsequent multi-center clinical trial. Therefore, we will demonstrate our ability to recruit 40 ACL reconstructed patients and assess study retention and compliance.

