9.2 SAMPLE SIZE DETERMINATION

This is a pilot study, with the purpose of discerning parameter estimates for use in powering a subsequent multi-center clinical trial. To estimate statistical power for this pilot design, we consider a comparison of outcomes by group across time. Previous studies have not examined the knee extension moment limb symmetry index, therefore the difference in knee joint position and the knee extension moment will be employed as proxy variables in order to estimate statistical power for this pilot design. We considered a comparison of outcomes between pre- and post-intervention^{17,18} and side-to-side differences in ACL-R patients. (Table 4).¹⁵

Using 2-sided testing between groups based on previous results, we will need 14 patients overall randomized at 1:1 ratio assuming 80% power to detect a significant difference in the knee extension moment between the groups with $\alpha=0.05$.¹³ Therefore, with recruitment of 40 subjects (goal of retaining 30

Table 4: Sample Size Calculations (N=sample size per group)

	Pre-intervention	Post-intervention	Sample Size
Peak Knee Extension Moment ¹⁰	3.7 ± 0.9	2.4 ± 0.5	N=7
Peak Knee Flexion ¹⁸	88.8 ± 8.0	105.0 ± 5.6	N=5
	Control	Intervention	Sample
Knee Flexion Angle ¹⁸	83.5 ± 20.5	103.8 ± 16.3	N=15
Vertical ground reaction force ¹⁸	2.0 ± 0.4	1.6 ± 0.3	N=14

subjects through study completion), we are adequately powered to declare significance. Thus, while not the primary purpose of this experiment, we are adequately powered to declare significance between groups.

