9.4 STATISTICAL ANALYSES

9.4.1 GENERAL APPROACH

- For descriptive statistics the results will be reported as percentages as well as means and standard deviations as appropriate for the measure. Categorical data will be reported as percentages while continuous data will be reported as means with standard deviations as well as data ranges.
- For inferential tests, indicate the p-value and confidence intervals for statistical significance (Type I error) and whether one or two-tailed.
- Checks for the assumption of normality will be performed prior to additional statistical procedures. If this assumption is not met then corrective procedures will be applied such as transformation or nonparametric tests as appropriate.

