9.4.2 ANALYSIS OF THE PRIMARY EFFICACY ENDPOINT(S)

The goal of the proposed study is to determine the impact of an innovative biofeedback training program on decreasing risk factors for secondary ACL injuries in adolescent athletes. Based on

previous work, the primary variable of interest and a surrogate for secondary ACL injury risk will be the knee extension moment limb symmetry index (LSI). The previously established movement asymmetry risk factors³² and therefore the primary measures of interest are the knee extension moment, vertical ground reaction force, and frontal plane knee range of motion. Symmetry between the operative and non-operative limbs in this study will be determined by calculating the limb symmetry index (LSI). Asymmetry in the peak knee extension moment has been identified as significant predictors of secondary ACL injuries (therefore reduction in this asymmetry will decrease the risk for secondary ACL injuries).³²

For **Aim 1** of this pilot study a within subject repeated measures assessment (ANOVA), as implemented under mixed models, will be used to determine if a clinical (LSI>90%) and/or statistical difference exists between the pre- and the two post-intervention time points (efficacy and durability) for the primary outcome of interest (knee extension moment asymmetry). Post-hoc testing will be completed for any variable that is determined to be statistically different.

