9.4.9 EXPLORATORY ANALYSES

Over the course of the study secondary outcomes will be examined to determine any mediating effects these variables may have, which could explain differences across time (**Table 3**). Secondary outcomes will be evaluated using exploratory analyses in order to generate hypotheses for future studies. These exploratory analyses will be conducted using linear mixed models.^{23,35,36} We will test both primary and secondary outcomes at an alpha level of 0.05 and will not control for potential Type-I errors due to multiple testing, using Bonferroni or Hochberg criteria,^{8,9,19} due to the pilot nature of this study. If an effect is declared 'significant' we will provide a cautionary note in resulting publication, as to the exploratory nature of the findings.

Table 3: Outcome Measurements

Primary Outcomes
Peak Knee Extension Moment Symmetry
Secondary Outcomes
Peak Vertical Ground Reaction Force Symmetry
Vertical Ground Reaction Force Impulse Symmetry
Frontal Plane Knee Range of Motion
Peak Knee Flexion Angle Symmetry
Peak Knee Flexion Angle
Peak Knee Valgus

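### The primary between-arm analysis of knee extension moment LSI is not tied to one scale or one model, and no stated form adjusts for baseline LSI

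*Combined protocol and SAP*

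**What the plan says.** Section 9.1 covers the comparison of the arms in general terms: "Depending on the outcome, change (completion-baseline), or the value at completion will be assessed". Significance can then be assessed by "a t-test or the non-parametric equivalent (2-sample Wilcoxon" test. No section assigns the knee extension moment LSI, or any other variable, to one of the two scales. Section 9.4.1 adds a normality check, with no named test or threshold; if it fails, "corrective procedures will be applied such as transformation or nonparametric tests as appropriate".

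For the primary endpoint, section 9.4.2 names something else: "a within subject repeated measures assessment (ANOVA), as implemented under mixed models". It compares the baseline visit with the two later visits. No group term, group-by-time contrast or baseline covariate is mentioned.

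Baseline LSI appears elsewhere only as an eligibility measure (5.2, criterion 16; 8.2). It is neither a stratification factor (6.3) nor among the possible confounders to be explored (9.4.7). Randomisation follows the first biomechanical assessment (6.3), so every eligible randomised participant should have the value.

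**The concern.** Two sections describe two analyses of the same endpoint. One is a between-arm comparison on an unstated scale; the other, as worded, contains no comparison of arms. A reader cannot tell which estimate will be the trial's result.

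None of the stated forms makes good use of baseline LSI. The final value ignores chance baseline imbalance, which matters with about 15 completers per arm. The change score subtracts the whole baseline value, which over-corrects unless the correlation is high. Section 9.4.2 does not recover the loss. If an unconstrained group-by-time term is added, its baseline-to-follow-up contrast equals the change-score comparison when data are complete.

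At stake are the precision of the arm comparison and the meaning of the standardised difference. Sections 9.1 and 9.2 give the powering of a later trial as the purpose of these estimates.

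**Working it through.** **Inputs from the documents.** Alpha 0.05 (9.4.9: "We will test both primary and secondary outcomes at an alpha level of 0.05"). Two-sided testing, 14 patients overall, 1:1 (9.2: "Using 2-sided testing between groups based on previous results, we will need 14 patients overall randomized at 1:1 ratio"). Power 80% (9.2: "assuming 80% power to detect a significant difference in the knee extension moment between the groups"). Recruitment 40, retention goal 30 (9.2: "Therefore, with recruitment of 40 subjects (goal of retaining 30"), so 15 per arm.

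**Assumptions.** The correlation rho between baseline and follow-up LSI is not given; 0.3, 0.5 and 0.7 are shown. Equal SDs at both times and, for illustration, a true difference of 0.8 SD are also assumed.

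**Step 1: the plan's own figure.** For the knee extension moment row of Table 4, SD = sqrt((0.9² + 0.5²)/2) = 0.728 and d = (3.7 − 2.4)/0.728 = 1.79. A two-sample t-test at two-sided 0.05 and 80% power needs 7 per group, 14 overall. The same method gives 5, 15 and 14 for the other rows, so all of Table 4 is reproduced. The sample size is thus an unadjusted two-sample calculation with no baseline correlation in it.

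**Step 2: variance relative to the final-value comparison.**
- Final value: 1.
- Change: 2(1 − rho).
- Baseline-adjusted (ANCOVA): 1 − rho².

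| rho | Change | ANCOVA | ANCOVA vs final value | ANCOVA vs change |
|---|---|---|---|---|
| 0.3 | 1.40 | 0.91 | 9% lower | 35% lower |
| 0.5 | 1.00 | 0.75 | 25% lower | 25% lower |
| 0.7 | 0.60 | 0.51 | 49% lower | 15% lower |

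**Step 3: the cost of estimating the slope.** With n per arm, ANCOVA variance is multiplied by about 1 + 1/(2n − 4), which is 1 + 1/26 = 1.038 at n = 15. Break-even with the final value is at (1 − rho²) × 1.038 = 1, so rho is about 0.19. The worst case is rho = 0, where variance is about 4% higher.

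**Step 4: power at 15 per arm, true difference 0.8 SD** (noncentral t; 28 df, or 27 for ANCOVA).

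| rho | Change | Final value | ANCOVA |
|---|---|---|---|
| 0.3 | 43% | 56% | 58% |
| 0.5 | 56% | 56% | 67% |
| 0.7 | 78% | 56% | 83% |

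At the plan's proxy effect of 1.79 SD, all three forms exceed 97% for rho from 0.3 to 0.7.

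**Step 5: the standardised difference.** The SD of change is sqrt(2(1 − rho)) times the final-value SD: 1.18, 1.00 and 0.77. A true 0.8 SD on the final-value scale therefore reads as 0.8/1.18 = 0.68, 0.80, or 0.8/0.775 = 1.03 on the change scale. Required sample size scales with the variance factor: 1.4, 1.0 or 0.6.

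**Step 6: type I error** (simulation under no effect, 15 per arm). Choosing t or Wilcoxon by a normality pre-check on one fixed scale gives 4.4% to 5.4%. Reporting the smaller p of the change and final-value t-tests gives about 9% with normal data (7.0% to 9.3% when skewed data are included).

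**The case against.** The strongest reply is that nothing here is invalid. Under randomisation the change and final-value comparisons are both unbiased. Section 9.2 says significance is not the main purpose, and 9.4.9 promises a caution on any significant effect. The size of the gain rests on a correlation and an effect that the documents do not give. Excluding patients with baseline LSI of 90% or more truncates the baseline and probably lowers rho, and at the plan's proxy effect power is ample in every form. All of this stands. It makes the point an efficiency and clarity improvement. It does not settle which scale applies or reconcile 9.1 with 9.4.2, and the proxy effect is for the moment, not the LSI.

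Four stronger readings are tempting, and the documents do not support them:
- *That the results will decide the scale and inflate type I error.* In 9.1 the word outcome most naturally means the variable, not the result. The figure of about 9% needs smallest-p reporting, which no section plans.
- *That the normality check inflates type I error.* On a fixed scale it stays near 5% (step 6).
- *That a switch to Wilcoxon or a transformation loses the mean and SD in LSI units.* Section 9.4.1 reports means and SDs for continuous data whatever the test, and 9.1 adds standardised differences.
- *That adjustment makes good the whole planned loss from 40 to 30.* This is so only near rho = 0.5, where 30/0.75 = 40, or 30/(0.75 × 1.038) = 38.5 with the finite-sample factor. At rho = 0.3, against the final value, it is 32 to 33.

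**Conclusion.** The point holds as a free improvement that should be made; it does not invalidate the trial. The documents leave the scale of the primary between-arm comparison open, give a second model without an arm term, and never adjust for baseline LSI. Baseline adjustment is never materially less precise than the stated forms (about 4% more variance at worst). For rho of 0.3 to 0.7 it reduces variance by 9% to 49% against the final value and by 35% to 15% against change. The gain over the final value vanishes at rho of about 0.2 or less. These sizes assume equal SDs, and the power figures also assume a 0.8 SD effect.

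The consequence that needs least assumption is for the next trial: a standardised difference without a stated scale cannot be used safely, because the required sample size differs by the factor 2(1 − rho).

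**What to change.** Rewrite 9.1 and 9.4.2 to name the same primary between-arm model:
- Responses: LSI at week 6 and week 12.
- Terms: arm, visit, arm-by-visit and baseline LSI (by visit), with the stratification factors as far as about 30 completers allow.
- Primary contrast: the arm difference at one visit, named in advance. The hypothesis in 9.1 refers to 6 weeks after the intervention, which is the week 12 assessment.
- Report: the adjusted mean difference in LSI units with its 95% CI. State which SD any standardised difference uses, and give the observed baseline-to-follow-up correlation.
- Sensitivity analyses: unadjusted change, unadjusted final value and rank-based results. For the primary endpoint, the normality check in 9.4.1 should lead to these and not replace the primary estimate.

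The cost is SAP wording, one or two degrees of freedom for baseline LSI, and a few more for the stratification factors. No new data are needed.

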The Biofeedback Approach to Recovery: Our proposed biofeedback approach has its foundation in retraining programs that were developed and implemented for primary ACL injury prevention. These retraining programs are designed to alter lower extremity mechanics through retraining landing mechanics, a very dynamic and complex task.²⁸ Such programs have proven effective for primary ACL tears: they decrease the risk factors for injury,^{20,28,29,40} however they have not decrease the incidence of ACL tears since implementation^{11,20,29,37,40}
Our novel biofeedback approach combines successful aspects of these existing programs with visual and tactile biofeedback. This strategy is further informed by recent work that examined the use of visual biofeedback to reduce loading asymmetry.²⁶ This work demonstrated that loading asymmetry could be attenuated using squatting tasks and visual biofeedback.²⁶ Current therapy interventions focus on muscle strength and range of motion and are ineffective in decreasing the incidence and risk factors for secondary ACL injuries. This proposal will be the first to implement a biofeedback training program in an ACL reconstruction population. If successful, this work will have a significant impact: it will provide the first retraining program that directly targets and effectively decreases known risk factors for secondary ACL injury risk factors.

Significance of our Approach: With the large proportion and increased incidence of ACL tears in adolescent athletes, it is imperative that we develop interventions to decrease the risk of secondary injuries and improve outcomes. Therefore, the **goals of the proposed study** are to determine the immediate impact of a biofeedback training program on decreasing risk factors for secondary ACL tears and determine if the impact is retained 6 weeks post-intervention. This study will also demonstrate our ability to recruit and retain post-operative ACL reconstruction patients until the completion of the novel biofeedback intervention and to assess their compliance with completing all of the exercises at each training session. In addition, we will determine the psychometric properties of the primary outcome measures, which have been previously identified as risk factors for a secondary ACL injury. This study will provide the foundation for the design and development of future studies that could shift the post-operative rehabilitation paradigm to include the assessment and normalization of

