3 OBJECTIVES AND ENDPOINTS

OBJECTIVES	ENDPOINTS	JUSTIFICATION FOR ENDPOINTS
Primary		
Determine the impact of a biofeedback training program on decreasing asymmetrical peak knee extension moment.	Peak Knee Extension Moment Symmetry	Peak knees extension moment asymmetry between the operative and non-operative side is a known risk factors for secondary ACL injuries and is therefore being used as the primary outcome to determine the ability of the biofeedback intervention to decrease a risk factor for secondary ACL injury risk.
Secondary		
To demonstrate our ability to recruit, retain and determine patient compliance in completing a biofeedback retraining program.	
 • Number of intervention sessions attended (compliance) • Number of missed biomechanical assessment time points (retention) 	This is a pilot clinical trial in which we need to determine both compliance with the biofeedback intervention as well as subject retention through the end of the study in order to appropriately plan for a future multi-center clinical trial.
Tertiary/Exploratory		
Determine the impact of a biofeedback training program on decreasing asymmetrical vertical ground reaction forces, frontal plane knee range of motion and the association between each of these measures and the change in the peak knee extension moment symmetry.	
Exploratory Endpoints:
 
 • Peak Vertical Ground Reaction Force Symmetry • Vertical Ground Reaction Force Impulse Symmetry • Frontal Plane Knee Range of Motion • Peak Knee Flexion Angle Symmetry • Peak Knee Flexion Angle • Peak Knee Valgus 	The peak knee extension moment is a known risk factor for secondary ACL injury risk, however, it is challenging to collect this measure in a clinical setting as it requires the collection of synchronized three-dimensional kinematic and kinetic data. Therefore, these exploratory endpoints will be assessed to determine their association with the change in symmetry in the peak knee extension moment. Through this analysis we hope to be able to identify additional measures to use in assessing this biofeedback intervention that will be more easily implemented in the clinical setting.

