7.2 PARTICIPANT DISCONTINUATION/WITHDRAWAL FROM THE STUDY

Participants are free to withdraw from participation in the study at any time upon request. An investigator may discontinue or withdraw a participant from the study for the following reasons:

- Pregnancy
- Significant study intervention non-compliance
- If any clinical adverse event (AE), or other medical condition or situation occurs such that continued participation in the study would not be in the best interest of the participant
- If the participant meets an exclusion criterion (either newly developed or not previously recognized) that precludes further study participation
- Study participant sustains an ACL tear of either limb
- Participant unable to attend the ACL Biofeedback intervention session for 2 days/weeks

The reason for participant discontinuation or withdrawal from the study will be recorded on the Case Report Form (CRF) (MOOP Appendix K). Subjects who sign the informed consent form

and are randomized but do not receive the study intervention may be replaced. Subjects who sign the informed consent form, and are randomized and receive the study intervention, and subsequently withdraw, or are withdrawn or discontinued from the study, will be replaced.

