9.4.3 ANALYSIS OF THE SECONDARY ENDPOINT(S)

For **Aim 2**, we will calculate rates of recruitment, retention and compliance. No hypothesis tests will be performed. However, correlates to these metrics will be assessed. For each of the outcome measures the between session analysis will allow us to calculate test-retest reliability. The use of correlations will allow us to compute criterion and predictive validity.

Study retention will be defined as a subject who attends each of the biomechanical testing session (baseline, immediately following intervention (intervention)/6 weeks after baseline (control), and then 6 weeks after training (intervention) or 12 week after the baseline (control). Proportion retention will be computed by dividing the number of retained subjects at the end of the intervention by the total number of patients randomized into the study. Compliance with the intervention will be defined as a subject who attends at least 80% of the biofeedback training sessions during the six weeks of the intervention. Proportion adherence will be computed by dividing the number of sessions attended by the total number training sessions (number of training sessions n=12).

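### The efficacy hypothesis and one sentence in 9.4.2 claim an effect on ACL injury risk, but the trial can test only a biomechanical surrogate

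*Combined protocol and SAP*

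**What the plan says.** The hypothesis appears in 4.1 under Aim 1 and again in 9.1 under the primary efficacy endpoint. In both places it begins: "We will test the hypothesis that our biofeedback program will decrease the risk of secondary ACL injury". Quoted further, it reads: "We will test the hypothesis that our biofeedback program will decrease the risk of secondary ACL injury by improving loading and movement symmetry". It goes on to name landing from a jump as the task and 6 weeks post intervention as the time.

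Section 9.4.2 describes the endpoint in two ways. It first says that "the primary variable of interest and a surrogate for secondary ACL injury risk will be the knee extension moment limb symmetry index (LSI"). A few lines later, a parenthesis draws the conclusion: "therefore reduction in this asymmetry will decrease the risk for secondary ACL injuries".

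Elsewhere the plan stays at surrogate level:

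- Section 3 sets the primary objective as reducing asymmetry in the peak knee extension moment. Its endpoint is "Peak Knee Extension Moment Symmetry".
- The overview in 4.1 gives the goal as an effect on surrogate measures of injury risk.
- The synopsis speaks of lowering a known risk factor.

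Section 2.2 says that the approach is founded on retraining programmes built to prevent primary ACL injury. It reports that they lowered the risk factors, but adds: "however they have not decrease the incidence of ACL tears since implementation".

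Under 7.2, one reason for which an investigator may withdraw a participant is: "Study participant sustains an ACL tear of either limb".

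**The concern.** A hypothesis should name something that the trial measures. Here it names injury risk, and what is measured is landing mechanics. The parenthesis in 9.4.2 supplies the missing step as an established consequence. With both in place, a significant change in symmetry would formally support a conclusion about injuries that no analysis in the trial addresses.

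This matters because the participants are aged 14 to 21 and plan to return to sport, and because the pilot is meant to shape a multi-centre trial. Whether changing this surrogate changes tears is a question for later work. The pilot's plan should not answer it in advance.

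**Working it through.** **1. What is measured.** Section 3, the synopsis and Table 3 in 9.4.9 list the endpoints. For Aim 1 they are knee extension moment symmetry, peak vertical ground reaction force symmetry, vertical ground reaction force impulse symmetry, frontal plane knee range of motion, knee flexion angle and its symmetry, and knee valgus. For Aim 2 they are sessions attended and assessments missed. None is an ACL tear.

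**2. Where a tear would appear.** It would be recorded as an adverse event (8.3.1, 8.3.4) and, if the investigator used the discretion in 7.2, as a reason for withdrawal. Events of special interest are marked not applicable (8.3.8). No section plans a comparison of tears between arms.

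**3. How long each participant is observed.** Assessments are at baseline, week 6 and week 12, and the synopsis gives participant duration as about 12 weeks. The 2-year figure is for the whole study. Inclusion criterion 3 in 5.1 places enrolment within about 6 weeks of readiness for release to full sport. At the outer end of that window, about 12 − 6 = 6 weeks of follow-up come after expected release. (Section 5.5 describes participants as already released, in which case all 12 weeks would count. The conclusion is the same either way.)

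**4. What the sample size is for.** Section 9.2 states 14 overall, 7 per group, for the peak knee extension moment at 80% power and two-sided alpha 0.05. The moment serves there as a proxy for its symmetry index. The inputs from Table 4 are 3.7 (SD 0.9) and 2.4 (SD 0.5).

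- Pooled SD = √((0.9² + 0.5²)/2) = √0.53 = 0.728
- Difference = 3.7 − 2.4 = 1.3
- Standardized difference = 1.3/0.728 = 1.786
- Two-sample t-test (noncentral t): 6.05 per group, rounded up to 7, so 14 overall

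The stated figure reproduces exactly. (The normal approximation gives 5 per group, so the t version is the one that matches.) The calculation concerns a moment. Nothing in 9.2 concerns injuries.

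**5. The statements side by side.**

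| Place | Level of the statement |
|---|---|
| Section 3, primary objective | Knee extension moment asymmetry |
| 4.1 overview | Surrogate measures |
| 4.1 Aim 1 hypothesis | Injury risk, by way of symmetry |
| 9.1 hypothesis | Injury risk, by way of symmetry |
| 9.2 sample size | Knee extension moment |
| 9.4.2, description of the primary variable | Surrogate |
| 9.4.2, parenthesis | Injury risk, stated as fact |

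The three injury-level statements are the exceptions.

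**6. The comparator.** Restating the hypothesis means naming what is compared. Section 9.1 describes group differences tested by a t-test or Wilcoxon test, and 9.2 describes two-sided testing between groups. Section 9.4.2 describes a within-subject repeated measures model comparing the pre-intervention assessment with the two later ones, and does not mention arm. These need to agree, or the reworded hypothesis will still not match its analysis.

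**The case against.** The strongest reply is that the hypothesis sentence, read to its end, is about symmetry. It names knee extension moment asymmetry, sits under the primary efficacy endpoint and is followed by the limb symmetry formula. Section 3 is the formal statement of objectives and is correctly worded. All of this stands. It shows that the intended test is sound, and that the fault lies in the wording of the claim and in the inference. It does not remove the parenthesis in 9.4.2, which has no qualification.

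Section 9.4.9 also promises a cautionary note with any significant effect, and 9.2 says that declaring significance is not the main purpose. These help in part. The note concerns multiple testing and the exploratory status of findings, not the step from a surrogate to injury.

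A reader might infer several stronger things that the documents do not support:

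- *That an injury analysis is planned or concealed.* None is described anywhere.
- *That 2.2 refutes the surrogate.* It concerns programmes for primary tears that retrained landing. This intervention trains squats after reconstruction. The passage is a caution by analogy, and the documents do not show what lies behind the incidence statement.
- *That validity will be computed against second injury.* Section 9.4.3 says "The use of correlations will allow us to compute criterion and predictive validity" but names no criterion, so this cannot be assumed.
- *That participants will be told of an injury benefit.* Section 8.3.7 promises a letter on study outcomes and makes no such claim.
- *That the number of tears expected in the trial measures the problem.* The only rate given, up to 29% in 2.2, has no time period, and no tear analysis depends on it.

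**Conclusion.** The point holds as an inconsistency between the claim and the design. Two statements of the hypothesis (4.1, 9.1) and one parenthesis (9.4.2) assert an effect on injury risk, while the endpoints, the sample size and the primary objective in Section 3 address a biomechanical surrogate. As worded, a symmetry result would be taken to support a conclusion that the design cannot test.

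The effect is on what may be concluded. The endpoint, data collection and sample size are untouched. The conclusion rests on the endpoint lists, the absence of any planned tear analysis and the 12-week participant follow-up. It needs no assumed tear rate and no judgement on whether the surrogate is valid.

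**What to change.** 1. In 4.1 and 9.1, restate the hypothesis to match Section 3, keeping the time point and naming the comparator: *the biofeedback program improves knee extension moment symmetry during landing from a jump 6 weeks post intervention, compared with attention control.*
2. In 9.4.2, describe the mixed model so that it delivers that comparison, for example as the difference between arms in change from baseline to the assessment 6 weeks post intervention, with the assessment immediately after training reported alongside. This brings it into line with the group comparison in 9.1 and 9.2.
3. In 9.4.2, delete the parenthesis containing "therefore reduction in this asymmetry will decrease the risk for secondary ACL injuries" and state that no conclusion about injury risk will be drawn from this trial. The experience reported in 2.2 can be cited as a reason for caution, by analogy.

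The cost is an amendment to the text and a narrower headline claim. Item 2 settles which comparison is primary, so the project statistician should confirm it. No data, procedure or sample size changes.
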